4.1. Sample Size

The sample size has been calculated assuming a 30% sustained remission rate on the placebo plus 6-month prednisone arms versus a 70% rate on the sirukumab plus 6-month prednisone arms at Week 52. To be able to detect that difference using a 5% significance level, the sample size of N=51 on sirukumab 100 mg SC q2w, N=34 on sirukumab 50 mg SC q4w, and N=34 on placebo when used in combination with a 6-month prednisone taper has > 91% power.

The study is also powered to detect a statistically significant difference between sirukumab 100 mg SC q2w plus 3-month prednisone (Arm B) and placebo SC q2w plus 6-month prednisone (Arm D) only if the assumptions for 6-month prednisone taper apply to the 3-month prednisone taper (i.e. 70% sustained remission rate at Week 52).

Subjects will be assigned to study treatment arms using an allocation ratio of 3:3:2:2:2. The randomization will be stratified by Baseline oral prednisone dose (<30 mg/day or ≥30 mg/day).

A sample size sensitivity analysis was performed to assess the effect on power if the sirukumab plus 6-month prednisone response rate was lower than expected at 65%, 60%, or 55%.

Table 4 Sample Size Sensitivity Analysis

Response Rate Sirukumab 100 mg + 6-Month Prednisone	Difference Active-Placebo	N Placebo +6- Month Prednisone	N Sirukumab 100mg + 6-Month Prednisone	Power
70%	40%	34	51	96%
65%	35%	34	51	89%
60%	30%	34	51	79%
55%	25%	34	51	64%

Assuming a placebo response rate of 30%, the target sample size of 34 for placebo SC q2w plus 6-month prednisone and 51 for sirukumab 100 mg SC q2w plus 6 month prednisone, a treatment difference larger than 21% will achieve statistical significance at the alpha=0.05 level.

No sample size re-estimation will be performed.

Given study termination, actual sample size will be the number of randomized subjects at study termination.

4.2. Randomization, Stratification and Blinding

Central randomization will be implemented in this study. Subjects will be randomized in a ratio of 3:3:2:2:2 and assigned to 1 of 5 treatment arms in accordance with the computer-generated randomization schedule generated prior to the start of the study, using validated software. Randomization will be performed by an Interactive Response Technology System. Once a randomization number has been assigned to a subject, it will not be re-assigned.

Randomization will be stratified by baseline oral prednisone dose (<30 mg/day or ≥ 30 mg/day). The number of relapsing/refractory subjects will be capped at approximately 50% to ensure that a sufficient number of subjects with new onset disease are recruited.

Blinding will be maintained during the 52-week double-blind treatment phase of this study by the provision of sirukumab and matching placebo for sirukumab in prefilled syringes in a matching presentation. Blinding to the prednisone dose during the taper will be maintained by providing prednisone doses below 20 mg in numbered blister packs. Depending on the subject's assignment to either the 3-, 6-, or 12-month taper, the over-encapsulated dose may or may not contain prednisone. The blister packs contain a combination of over-encapsulated 10 mg, 5 mg, and/or 1 mg prednisone tablets with cellulose filler to prevent rattling and/or placebo capsules containing only the filler. Each subject, regardless of treatment arm, will be provided the same number of capsules per day for a given week to maintain the blind.

Blinding during the q4w dosing regimen will be maintained by the provision of placebo for sirukumab such that subjects randomized to this arm will follow a q2w dosing regimen but alternate between active (starting at Baseline) and placebo treatments for the duration of the 52-week, double-blind phase.

Investigators and the sponsor/study team will remain blinded to the results of the fasting lipids, CRP and ESR laboratory tests after the start of treatment. Investigators and the study team will have access to Screening and Baseline values, and will thereafter remain blinded to these results until the end of Part A. Alerts will be provided by the central laboratory for abnormal, clinically significant findings to enable investigators to manage subject safety. Since the ESR is measured at the site, an unblinded assessor at the local laboratory will report the ESR results. The investigator will be notified of the value of the ESR result when an ESR result is >40 mm/hr in order to determine if a treatment change is warranted. Investigators are advised to consider these notifications of an elevated ESR which has reached the alert value as an additional element in the determination of whether a subject is experiencing GCA disease flare. An elevated ESR in isolation should not be the sole basis for investigator assessment of disease flare, particularly in the absence of clinical symptoms (e.g. cranial or polymyalgia rheumatic [PMR]) suggestive of disease activity.

Due to the sponsor's decision to terminate the study, to facilitate patient management, treatment codes for the blinded prednisone study drug will be broken and provided to the investigator at the Early Withdrawal Visit, when occurring after sponsor's decision to terminate the study. Treatment codes for the subcutaneous investigational product (sirukumab or placebo) will be unblinded at the end of the study, after database lock. However, unblinding for the subcutaneous investigational product can be requested for individual subjects at any time for safety management. In addition, CRP value from the Early Withdrawal Visit will be provided to the investigator to facilitate subject management.

4.3. Analysis Set

The following analysis sets will be used for Part A summaries. Part B analysis sets are defined in [Section 11.1](#).

4.3.1. All Subjects Screened

The All Subjects Screened Set will consist of all the subjects who have been screened for enrollment in the study regardless of whether they were enrolled into the study. This set will be used for summarizing reasons for screen failures.

4.3.2. Randomized

The Randomized set will consist of all subjects who meet study criteria and are randomly assigned to treatment in the study. In the event that there is a discrepancy, all subjects in the Randomized set will be analyzed according to the treatment they were randomized to receive and not according to what they actually received. The Randomized set will be used for summarizing the study, such as subject disposition.

4.3.3. Intent-to-Treat

The Intent-to-Treat (ITT) set will include all randomized subjects who received at least 1 dose of SC investigational product (IP). In the event that there is a discrepancy, all subjects in the ITT set will be analyzed according to the treatment they were randomized to receive and not according to what they actually received. The ITT set will be used for the primary efficacy analysis and all other efficacy endpoints.

4.3.4. Safety

The Safety set will include all randomized subjects who received at least 1 dose of SC IP. All subjects in the Safety set will be analyzed according to the treatment actually received and not according to the treatment they were randomized to receive, in the event there is a discrepancy. The Safety set will be used to analyze all of the safety endpoints.

4.4. Analysis Visits

Data will be presented and analyzed according to the visit recorded in the database. For other efficacy and safety data that visit are entered, no visit windows will be defined as sites should have case report form (eCRF) instructions and training to ensure reasonable data entry. If a visit happens outside the protocol-defined window (Week X \pm 3 days), one of the following will be occur:

- If it is recorded as Week X visit, no visit re-mapping will be done (except for PRO endpoints and Part B visits) and the recorded visit will be used in all analysis.
- If it is recorded as unscheduled visit, it will be treated as unscheduled visit.

In general, only those assessments which are assigned to an analysis visit will be included in the summary tables and figures and will be presented by visit. Unscheduled visits will not be included in summary tables or figures, with the following exceptions: if the table or figure includes data values for all post-baseline assessments (worst/best/maximum/minimum post-baseline assessments), or for tables which report the values during a period of time, unscheduled visits will be included. All unscheduled visits will be included in the listings.

When reporting results or events that are reported on an ongoing basis, such as cumulative prednisone dose or flare at Week X: All results/events will be taken into account that occur inclusively between the day after the Week X-1 visit and the day of the Week X visit. The actual day of the Week X visit will always be taken into account as the day of visit X, even if the actual visit occurred outside of planned visit window.

4.5. Definition of Baseline Value and Study Day

Baseline for Part A is defined as the last non-missing evaluation, including screening, re-screening and unscheduled assessments, prior to first SC IP, unless otherwise specified.

For assessments prior to the first SC IP date, the study day will be calculated as:

$$\text{Assessment date} - \text{First SC IP date}$$

For assessments on or after the first SC IP date, the study day relative to the Part A first SC IP date (i.e. the number of days from first dose date) will be calculated as:

$$\text{Assessment date} - \text{First SC IP date} + 1 \text{ day}$$

If the assessment date is completely missing or partial, the study day will be missing.

4.6. Handling of Missing Data

4.6.1. Treatment Failure Definition

For the primary endpoint derivation, a treatment failure is defined as any subject who:

1. Discontinued permanently SC IP prior to completing week 52 visit due to any reason and continued in the study (i.e. follow-up off treatment)
- or
2. Withdrew from the study for any reason earlier than 10th October 2017, the study termination date.

A subject will be considered a treatment failure from the earliest date that the subject meets any of the 2 treatment failure criteria. Only withdrawals prior to 10th October 2017 will be considered, withdrawals on or after this date will likely be result of study termination at sponsor's request and not provide an accurate summary of treatment response.

A subject that temporarily has their treatment of SC IP put on hold, will not be considered as permanent discontinuations.

4.6.2. Sustained Remission

4.6.2.1. Main Analysis

The following procedures will be used to handle missing data for derivation of sustained remission (i.e. endpoints mentioned in [Section 8.1](#) and [Section 8.2.2](#)):

1. Any subject who is classified as a treatment failure (as per definition of [Section 4.6.1](#)) will be considered as not achieving sustained remission for the primary efficacy analysis and the supportive analyses of the primary efficacy endpoint.

2. Subjects with all four of the components of the primary endpoint missing at two consecutive scheduled visits will be considered as not achieving sustained remission for these two visits.
3. Subjects with all the components missing at Week X ($X \neq 52$) visit will be considered as achieving sustained remission at Week X visit if achieving sustained remission at the neighboring visits; as not achieving sustained remission otherwise. Data recorded at unscheduled visits will be taken into account based on the unscheduled visit date and will be associated with the next scheduled visit occurring after the unscheduled visit date.
4. Subjects with at least one of the four components of the primary endpoint missing at Week 52 visit will be considered as not achieving sustained remission at Week 52 visit.
5. When only a subset of the components is missing at Week X visit, the rules will be applied to the components first and then the imputed components are used to impute the values at post-baseline values. Similar rules as for complete missing visits are applied:
 - a. Subjects with some components missing at 2 consecutive visits will be considered as not achieving sustained remission for the missing components at these 2 visits.
 - b. Subjects with some components missing at Week X ($X \neq 52$) visit will be considered as achieving sustained remission for the missing components at Week X visit if achieving sustained remission at the neighboring visits; as not achieving sustained remission otherwise
 - c. Subjects with some components missing at the Week 52 visit will be considered as not achieving sustained remission for the missing components at the Week 52 visit.

4.6.3. Cumulative Prednisone Dose over Time

4.6.3.1. Main Analysis

For the main analysis of cumulative prednisone dose over time (mentioned in [Section 8.2.1](#)), data from subjects who permanently discontinue SC IP prior to completing week 52 visit due to any reason and continue in the study will be used for the analysis. Cumulative prednisone dose will be set to missing once a subject withdraws from the study.

4.6.4. Missing Data Handling Rules

For cases where the baseline data is missing, no imputations will be performed.

GCA formal/suspected diagnosis Imputation Dates:

Time since formal diagnosis is defined as: Randomization date - formal diagnosis date + 1

Time since suspected diagnosis is defined as: Randomization date - suspected diagnosis date + 1

Partial dates for suspected/formal diagnosis recorded in the eCRF will be imputed using the following:

- If the day of suspected diagnosis is missing then day will be set to “01” month.
- If the month of suspected diagnosis is missing then month will be set to “January”.
- If either the day or month is missing for formal diagnosis then the following rules will be applied:

- If the day of formal diagnosis is missing then it will be set to “01” or to the day of suspected diagnosis, only if the year and month of suspected and formal diagnoses are equal – whichever is later.
- If the month of formal diagnosis is missing then it will be set to “January” or to the month of suspected diagnosis, only if the year of suspected and formal diagnoses are equal – whichever is later.

Concomitant Medication and Adverse Events Imputation Dates:

The following method will be used to impute missing dates for concomitant medications and adverse events (AE):

Missing start dates (where UK and UKN indicate unknown or missing day and month, respectively):

- UK-*MMM*-*YYYY*:
 - If the month and year are different from the month and year of first SC IP dose in Part A, assume 01-*MMM*-*YYYY*.
 - If the month and year are the same as the first study dose month and year and the stop/end date (after any imputation) is on or after first SC IP dose in Part A, then assume the date of first SC IP dose in Part A.
 - If the month and year are the same as first SC IP dose in Part A month and year and the stop/end date (after any imputation) is prior to first SC IP dose in Part A, then assume the stop/end date for the start date.
- DD-UKN-*YYYY*/UK-UKN-*YYYY*:
 - If the year is different from the year of first SC IP dose in Part A, assume 01-JAN-*YYYY* of the collected year.
 - If the year is the same as first SC IP dose in Part A year and the end date (after any imputation) is on or after first SC IP dose in Part A, then assume the date of first SC IP dose in Part A.
 - If the year is the same as first SC IP dose in Part A and the end date (after any imputation) is prior to first SC IP dose in Part A, then assume the end date for the start date.

Missing stop/end dates (where UK and UKN indicate unknown or missing day and month, respectively):

- UK-*MMM*-*YYYY*: Assume the last day of the month.
- DD-UKN-*YYYY*/UK-UKN-*YYYY*: Assume 31-DEC-*YYYY*.

In case of the death of the patients and the imputed end date is after the date of death, the stop/end date will be imputed as the date of death.

Completely missing dates will not be imputed.

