7.3. Prednisone Intake as a Concomitant Medication

All corticosteroid dosages recorded on the Concomitant Medications - Corticosteroids page in the eCRF will be converted to a prednisone-equivalent average daily dose (mg/day) using a conversion factor for each particular medication. The list will be updated throughout the course of the study to include all corticosteroids taken by the subjects and will be finalized prior to the database lock and unblinding. The conversions of all corticosteroids will be done based on standardized medication name and using the following information from online calculator <http://www.globalrph.com/corticocalc.htm>, retrieved on 24th January 2018

Concomitant Medications with Standardized Medication Name Including the Following Term	Conversion factor for Prednisone - Equivalent Dose (mg)
Cortisone	0,2
Hydrocortisone	0,25
Prednisone	1
Prednisolone	1
Triamcinolone	1,25
Methylprednisolone	1,25
Dexamethasone	6,67
Betamethasone	8,33

Only medications with a unit reported in ‘mg’ will be converted to prednisone.

DOSE2 (prednisone-equivalent dose in mg) = DOSE (collected dose in mg) x conversion factor

DD (daily dose in mg/day) = DOSE2 (prednisone-equivalent dose in mg) x frequency factor

The records from concomitant medication datasets will be mapped to weeks corresponding to the prednisone schedule, e.g. if a subject has prednisone as rescue therapy for 10 days, the first 6 days may be mapped to Week X and the rest of the 4 days will be mapped to Week (X + 1) based on the start and end dates of the rescue medication, as well as the start and end dates of the prednisone tapering schedule at each week.

The following information on corticosteroids taken will be presented in a listing:

- Start and stop dates
- Original units, frequency and dose
- Prednisone-equivalent daily dose (in mg)
- Whether or not it was taken as a rescue medication

- Reason for medication (as collected on the Concomitant Medication-Corticosteroid eCRF page).

Two categories of concomitant prednisone intake will be identified:

- Concomitant prednisone intake as rescue therapy: all concomitant intake of corticosteroids reported for which the question “Was drug administered as a rescue medication?” is “Yes”
- Concomitant prednisone intake for non-GCA-related reasons: all concomitant intake of corticosteroids reported for which the question “Non Giant Cell Arteritis (GCA) related” is ticked

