If any concomitant corticosteroid medication when the unit is not in (Actuation, Application, Area under curve, Cubic centimeter, Cells, Cells per kilogram, Fingertip unit, Drops, Gum, Inhalation, Kilocalories, Minimum alveolar concentration, Mega becquerels (MBq), Millicurie, Nebule, Patch, Powder, Puff, Ring, Spray, Suppository) or any of concomitant non-corticosteroid medication identified as “GCA related” with the question “Was drug administered as a rescue medication?” is ticked as “Yes” and if the first SC IP Date ≤ Concomitant medication start date ≤ Week 52 visit date, then subject will fail the criterion.

If all of the 4 criteria are met, subject will be considered in sustained remission at Week 52. If 1 of the 4 criteria is not met, the subject will be considered as not in sustained remission at Week 52.

For more details on imputation of missing data for the primary endpoint, please refer to [Section 4.6.2.1](#).

Given study termination, only the subset of subjects who attended the Week 52 visit or who discontinued study treatment or withdrew from study prior to the 10th of October 2017 will be included in this analysis.

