8.2. Secondary Efficacy Endpoints

8.2.1. Cumulative Prednisone Dose (Study Drug and Corticosteroid Rescue Therapy) over Time

Cumulative prednisone is the cumulative prednisone dose from the taper (both open-label and blinded) as well as from the corticosteroid rescue therapies, as defined in [Section 3.3](#) and [Section 7.3](#). Cumulative dose at Week X will be derived as the sum of all the doses from baseline to Week X. If a subject withdraw from study between two scheduled visits, all prednisone doses recorded between his last scheduled visit and study withdrawal will be associated to the next scheduled visit. For example, if a subject withdraw between the Week 24 visit and the Week 28 visit, all doses recorded after the day of Week 24 will be associated to Week 28. For more details on imputation of missing data for the key secondary endpoint, please refer to [Section 4.6.3.1](#).

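### For partially dated corticosteroid rescue records, the SAP's date rule makes successive dose steps overlap and be added together, overstating cumulative and rescue-only prednisone for those subjects

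*SAP*

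**What the plan says.** SAP 4.6.4 covers concomitant medications and adverse events together: "The following method will be used to impute missing dates for concomitant medications and adverse events (AE").

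**Starts.** With the day missing: "If the month and year are different from the month and year of first SC IP dose in Part A, assume" the first of that month. With the month missing: "If the year is different from the year of first SC IP dose in Part A, assume" 1 January. If the partial start falls in the month (or year) of the first subcutaneous dose and the record ends on or after that dose, the start becomes the first-dose date. If the record ended before that dose, "then assume the stop/end date for the start date".

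**Ends.** With the day missing: "Assume the last day of the month". With the month missing: 31 December. The one cap given there is the date of death. Completely missing dates are left missing.

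**Use in the dose endpoint.** SAP 7.3 converts each corticosteroid record to a prednisone-equivalent daily dose and assigns it to weeks "based on the start and end dates of the rescue medication" and of the taper weeks. SAP 8.2.1 then adds taper and rescue: "Cumulative dose at Week X will be derived as the sum of all the doses from baseline to Week X". The only protection against double counting is in SAP 7.1, and it concerns one medication mapped to several ATC terms.

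**Limits.** SAP 4.6.3.1 sets cumulative dose to missing after study withdrawal. SAP 4.4 counts ongoing data only up to the day of the visit.

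**Criterion 4 of the primary endpoint (SAP 8.1).** For a rescue-ticked medication, "if the first SC IP Date ≤ Concomitant medication start date ≤ Week 52 visit date, then subject will fail the criterion".

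**The concern.** Taking the widest interval is sensible when the question is whether an event was treatment-emergent or a medication was concomitant. It does not suit adding up milligrams, because every imputed day carries a dose. A rescue course is often several records, one per dose step. If the step dates are partial and fall in the same month, each step is given up to the whole month and the steps are added as if taken together.

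A start with unknown month in the first-dose year goes back to the first injection. It then lies on top of taper doses already counted, although Protocol 4.2.1 and 6.3 say that subjects who cannot follow the taper cease the blinded prednisone when rescue is offered.

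For these subjects the by-visit cumulative dose and the rescue-only dose would be too high. Protocol 9.3.3 names cumulative prednisone at Week 52 as the key secondary endpoint, so it will be read with interest even though it is now only described.

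A second gap affects the primary endpoint. A rescue-ticked record with no start date cannot satisfy a condition on its start date, so it does not by itself make the subject fail criterion 4.

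**Working it through.** The plan states no figure for this quantity, so there is nothing to reproduce. The check applies the 4.6.4 dates, the 7.3 week mapping and the 8.2.1 sum to assumed rescue courses. The total is the sum over records of daily dose × days from imputed start to imputed end.

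**1. Scale (SAP Table 3, 6-month column).** The blinded steps sum to 116 and the open-label steps from 60 to 20 sum to 260. From a 20 mg start: 7 × (20 + 116) = 952 mg. From a 60 mg start: 7 × (260 + 116) = 2632 mg.

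**2. Three steps in one 30-day month, all days unknown** (assumed 60, 50, 40 mg/day, 10 days each, not the first-dose month).
- True: 10 × (60 + 50 + 40) = 1500 mg.
- By the rule: 30 × 150 = 4500 mg, three times the true dose. The excess of 3000 mg is more than the whole 6-month taper from 60 mg.

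**3. Four weekly steps from the 1st of a 31-day month** (assumed 40, 30, 25, 20 mg/day). True: 7 × 115 = 805 mg.
- Start day missing only: 7×40 + 14×30 + 21×25 + 28×20 = 1785 mg (2.2 times).
- End day missing only: 31×40 + 24×30 + 17×25 + 10×20 = 2585 mg (3.2 times).
- Both missing: 31 × 115 = 3565 mg (4.4 times).
- If only one step may count on any day, the month's total must lie between 31 × 20 = 620 mg and 31 × 40 = 1240 mg. An equal split gives 31/4 × 115 = 891 mg.

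**4. Month unknown on both dates** (assumed first dose 1 March 2016, 28 days at 20 mg in 2016). True: 28 × 20 = 560 mg. By the rule, 1 March to 31 December is 306 days, so 306 × 20 = 6120 mg (10.9 times), all before Week 52.

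**5. Cases with little or no error.** Complete dates return the true dose. A single 20 mg step filling a 31-day month gives 620 mg either way. Six 28-day steps (40, 30, 20, 15, 10, 5 mg) from the 1st of a 31-day month, with days missing on both dates, go from 3360 to 6135 mg (1.8 times).

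**6. What an arm contrast could look like.** Assume the course in step 3, rescue in 70% against 30% of subjects, and a share f of courses with both days missing, equal in the two arms. The false difference in means is 0.4 × f × (3565 − 805): 0 mg at f = 0, 55 mg at 5%, 221 mg at 20% and 552 mg at 50%. The true rescue difference is 0.4 × 805 = 322 mg. Neither the rescue rates nor f are in the documents.

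**7. Criterion 4.** SAP 7.1 classes a medication with a completely missing start date as both prior and concomitant unless it ended before the first dose. SAP 4.6.4 leaves that start missing. SAP 8.1 tests whether the start lies between the first injection and the Week 52 visit, and a missing date cannot pass that test. The same record is therefore concomitant under 7.1 and not counted as rescue under 8.1. It also has no start from which to count days, so its dose is at risk of being left out: an error in the opposite direction.

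**The case against.** The strongest reply is that neither SAP 7.3 nor 8.2.1 cites 4.6.4. For missing data in this endpoint, 8.2.1 points to 4.6.3.1, which has no date rule. The cross-reference to 4.6.4 from the medication section sits in 7.1, just before the prior/concomitant classification. That is correct, so the link is an inference. But 4.6.4 is worded for all concomitant medications, and no other date rule exists for these records. If its dates were not meant to be used, the SAP would have no rule for a partially dated dose record.

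Several limits also stand:
- Death is not the only bound. Withdrawal (4.6.3.1) and the visit day (4.4) also cut the sum. Since early withdrawal visits were complete by 30 November 2017 (SAP 1.1), an imputed end of 31 December 2017 cannot add dose after withdrawal.
- Concomitant medications are reviewed at intervals of at most four weeks in Part A and at flare visits. The unknown-month example is therefore a constructed extreme.
- SAP Section 8 produces summary statistics only. The median and interquartile range are shown, study drug and rescue are shown separately, and the records are listed with their dates.
- A rescued subject will usually also fail criterion 2 or 3, so the criterion 4 gap should seldom decide the outcome alone. It is still a contradiction between two sections.

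A reader might infer that every concomitant medication is stretched. It is not: complete dates are untouched, completely missing dates are not imputed, and a record that ended before first dose may get its end date as its start.

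**Conclusion.** The point holds for partially dated corticosteroid rescue records. The 4.6.4 dates, fed through 7.3 and 8.2.1, overstate cumulative and rescue-only prednisone whenever steps share a month or year, or a back-dated start runs into the taper. In the assumed same-month courses with both days missing, the total is 3 to 4.4 times the true dose. It is less for longer steps and exact for complete dates. This rests on 4.6.4 governing the dates used for dose, which its general wording supports but no cross-reference confirms.

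A reader might also infer that placebo dose is inflated most and that the steroid-sparing effect of sirukumab is overstated. The documents do not support that. They give neither rescue rates by arm nor the frequency of partial dates; if Arm B's 3-month taper led to more rescue, the bias would run against sirukumab. Nor is a test result at risk, because none is planned in this SAP.

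The criterion 4 gap is separate and real, and probably decides few subjects. Both points should be corrected before lock.

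**What to change.** Add a rule for the dose derivation only, applied to partially dated records from the concomitant corticosteroid page:

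1. End a step no later than the day before the next recorded step starts. Start it no earlier than the day after the previous step ended or the last taper dose.
2. Cap the end at the visit cut-off, withdrawal or last contact, whichever is first.
3. Exempt records that validly alternate by day, such as the one-in-three and two-in-three-day frequencies in the SAP 7.3 table.
4. Where both boundary days are unknown, split the known interval equally, or add a summary using only completely dated records. In the three-step example the equal split gives 10 × 150 = 1500 mg.
5. In SAP 8.1, count a rescue-ticked record with a completely missing start date as failing criterion 4 unless its end date precedes the first subcutaneous dose. Carry the same rule into SAP 8.2.2.
6. State in 7.3 and 8.2.1 which date rule applies.

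Leave 4.6.4 unchanged for adverse events and for prior/concomitant classification. The cost is SAP wording and small changes to the dose and criterion 4 derivations before database lock. The bounds use record, visit and withdrawal dates, so no new data are needed.
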